Insulin administration has been shown to improve memory and learning in healthy people and in those with neurodegenerative diseases (see Table 1). Intranasal insulin has shown to have neuroprotective and restorative effects in several human clinical trials. In a recent randomized, double-blind, placebo-controlled study with over 100 people suffering from amnestic mild cognitive impairment or Alzheimer's Disease, intranasal insulin preserved cognitive function in both selective cognitive domains and more globally compared to placebo.³⁴ The insulin-treated patients also did not show a decline in measures of brain metabolism, whereas the placebo-treated participants did show decreases in fluorodeoxyglucose ¹⁸F uptake in various lobes (parietotemporal, frontal, precuneus, and cuneus). Further, improvements in episodic memory persisted for several weeks after treatment cessation. Overall, these findings suggest that intranasal insulin not only affects cognitive function acutely, but that over time, there may be associated structural changes that lead to a more permanent treatment benefit. Since cognitive dysfunction is very common in MS and can be devastating, a treatment intervention (i.e., intranasal insulin) that can help both acutely and longitudinally is worth pursuing.

| REF. | INTRANASAL INSULIN DOSE | SUBJECTS | ASSESSMENT |
|---------------|-------------------------------|-----------------|---|
| Benedict 2004 | 160 IU (long-term) | Healthy | Word list (immediate, delayed recall |
| Reger 2006 | 20 or 40 IU (acute) | Probable AD or | Story recall (immediate, delayed recall) |
| | | MCI vs. healthy | Word list (immediate, delayed recall) |
| Benedict 2007 | 20 IU Aspart vs. 20 IU | Healthy men | Word list (immediate recall) |
| | Regular (long term) | | Word list (delayed recall) |
| Benedict 2008 | 160 IU (acute) | Healthy, normal | Digit span, object location (immediate recall) |
| | | weight, no meds | Mirror tracing (immediate recall) |
| Hallschmid | 160 IU (long-term) | Obese men | Word list (delayed recall) |
| 2008 | | | Word list (immediate recall) |
| Reger 2008 | 20 IU (long term) | AD or MCI | Memory score (immediate/ delayed recall ratio) |
| | | | Voice onset time (immediate/delayed recall ratio) |
| Reger 2008 | 10, 20, 40, 6 0 IU | AD or MCI | Story recall (immediate recall or delayed recall) |
| | (acute) | vs. healthy | Word list learning (immediate & delayed recall) |

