Aim 1. Safety data will be analyzed as they are captured in real time. Assessments will focus on AEs (including study treatment tolerability assessments, laboratory evaluations, vital signs, and physical examination). The incidence rate of AEs will be recorded by system organ class, severity, and by relationship to the study treatment. Tolerability analysis will be based on the number (%) of subjects who failed to complete the study due to adverse events. Lab values for each parameter will be summarized by shift tables. For quantitative parameters, summary statistics for actual values and change from baseline will be presented. Changes in the first 24 weeks will be compared between groups using mixed effects regression analyses to account for the longitudinal nature of the data using random subject-specific intercepts and slopes.

Aim 2. Summary statistics (mean ± standard deviation, median and interquartile range, or number and percentages) will be used to characterize the outcomes. For each cognitive outcome, to evaluate variability in the estimated means across groups, assuming that the within-group means are normally distributed, a one-way ANOVA will be conducted at the follow-up visits during the first 24 weeks. If the within-group data are strongly non-Gaussian, a Kruskal-Wallis test will be used. A mixed effects longitudinal model will also be used to test whether any differences across groups exist at the follow-up visits within the first 24 weeks. Further, models accounting for covariates of interest, including the HOMA-IR, body composition, body mass index, age, sex and depression, will be used. For within-person changes in measures at follow-up compared to baseline, paired t-tests will be used. We will also evaluate the SDMT at each study visit and other MACFIMS outcomes at week48 to establish the longevity of any therapeutic response to insulin.

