Aim 3. For the biomarker outcomes, to evaluate variability in the estimated means across groups, assuming that the within-group means are normally distributed, a one-way ANOVA will be conducted at the follow-up visits during the active treatment phase. If the within-group data are strongly non-Gaussian, a Kruskal-Wallis test will be used. A mixed effects longitudinal model will also be used to test if differences across groups exist at follow-up visits. For within-person changes in measures at follow-up compared to baseline or before versus after calorie restriction days, paired t-tests will be used. Correlations between the biomarkers will be assessed. A bootstrap of subjects will be used to obtain 95% equal confidence intervals for these measures. We will also evaluate the biomarker changes after study therapy ends.

Sample Size and Power: Sample size estimates are difficult given the novelty of the project but are based on the goal of detecting a benefit of insulin on cognition. In a pivotal study of two doses of intranasal insulin versus placebo in participants with mild cognitive impairment or mild to moderate Alzheimer's Disease, the Dementia Severity Rating Scale score improved over the four-month treatment course in those receiving intranasal insulin.³⁴ Using the scores in the 10 IU twice a day group, given a two-sided alpha of 0.05 and beta 0.20 (80% power), assuming 3 follow-up cognitive tests and a correlation between baseline and follow-up results of 0.5, 29 subjects per group are required. To account for drop-outs and for the three-arm design, a total of 35 subjects per group is planned. With SDMT as the outcome, for a two-arm design, this sample size confers 80% power (assuming SDMT standard deviation of 9 points and two-sided alpha of 0.05) to detect a 6-point improvement in SDMT which seems reasonable considering that transcranial stimulation with cognitive training

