## VIII. Regression models: Modified intention to treat analyses

- a. Analyses will adjust for age, sex, and years of education. We will also incorporate variables with differences between the treatment arms that exceed 10% as identified using results of the descriptive analyses.
- b. For analytic models for each outcome, the primary hypothesis test will compare INI (regardless of dose) versus PLAC and will be conducted first. Secondary pairwise tests comparing LDINI versus PLAC, HDINI versus PLAC, HDINI will then be conducted.
- c. Analyses will first be conducted first through the week 24 measure (0, 6, 12, 24). Secondary analyses will include weeks 36 and 48 (0, 6, 12, 24, 36, 48) to evaluate a potential sustained effect post cessation of treatment.
  - i. The week 24 visit must have occurred within 25 weeks (i.e., the protocol outlines a 1 week visit window).
- d. Eligible participants for the primary analysis are those with baseline or screening SDMT data
- e. Missing values for key baseline covariates of interest is expected to be small; however, primary analyses will include a missing indicator level for the categorical variable if it is included in analytic models.

- f. For mixed effects models, time will be considered as a linear variable in primary analyses.
  - i. Sensitivity analyses will evaluate potential non-linearity in changes over time using appropriate methods (e.g., quadratic terms for time or splines).
- g. Primary outcome: change in SDMT using raw scores over time
  - i. Change in the raw SDMT score over time will be assessed using a linear mixed effects model with unstructured covariance structure, random intercepts. If model fit is improved with the addition of random slopes, they will be added. The term of interest will be the coefficient for the cross-product term between INI and time.
- h. Secondary outcomes
  - i. Adverse events
  - ii. Change from baseline cognitive function in the tests listed below.
    - Rate of change in each cognitive test will be assessed using a linear mixed effects model with unstructured covariance structure, random intercepts. If model fit is improved with the addition of random slopes, they will be added. The term of interest will be the coefficient for the cross-product term between INI and time.
  - iii. Change in multiple sclerosis (MS) functional composite (MSFC)

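### The primary SDMT test is an arm-by-linear-time slope with no stated use of baseline SDMT; it does not match the protocol's visit-level 6-point difference and is usually less efficient than a baseline-adjusted week-24 contrast.

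*SAP*

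**What the plan says.** SAP section VIII, items f and g, sets out the primary SDMT model: a linear mixed model on raw scores with random intercepts, and random slopes if they improve fit. In it "time will be considered as a linear variable in primary analyses". The tested term is the insulin-by-time cross-product, and the first analysis uses weeks 0, 6, 12 and 24. Quadratic terms and splines are sensitivity analyses only. The named covariates are age, sex and education, plus any variable that differs between arms by more than 10%. Week 0 enters as a response. The section does not say whether an arm main effect is fitted or whether arm means are constrained equal at baseline, and it names no contrast at week 24.

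The protocol frames the question as a difference in scores. Under Analytic Plan, Aim 2, a mixed model is used "to test whether any differences across groups exist at the follow-up visits within the first 24 weeks", beside a one-way ANOVA at those visits. Sample Size and Power gives 80% power "to detect a 6-point improvement in SDMT", "assuming SDMT standard deviation of 9 points and two-sided alpha of 0.05". The sample size itself comes from a dementia severity scale: "assuming 3 follow-up cognitive tests and a correlation between baseline and follow-up results of 0.5, 29 subjects per group are required", after which "a total of 35 subjects per group is planned".

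On time course, the Introduction says of earlier trials that "intranasal insulin not only affects cognitive function acutely", and the same sentence goes on to suggest structural change that builds over time.

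**The concern.** A straight line fitted from week 0 can represent an effect that accumulates evenly. It represents an effect that appears early and then holds less well, because the flat later stretch pulls the slope down. If the arm term is free, the model also treats any chance baseline difference between randomised arms as something to estimate, and so gives up precision that randomisation would allow it to keep.

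Two things are at stake. The first is power for the primary SDMT test. The second is the estimate: the end of Sample Size and Power says that the trial is not expected to be conclusive on cognition and is meant to supply estimates of change for phase III design. A slope that stands in for a week-24 difference could pass a distorted effect size to that next trial.

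**Working it through.** **Inputs.** From the protocol: SD 9, a 6-point effect, 35 per arm, two-sided alpha 0.05, 1:1:1 allocation. From the SAP: pooled insulin v placebo (70 v 35) and visits 0, 6, 12, 24. Assumed here: correlation r = 0.5 between visits, with a range up to 0.95, because the documents give 0.5 only for the dementia scale; 9 as a single-visit SD (the protocol does not say whether it is that or an SD of change); compound symmetry; complete data; normal-approximation power.

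**1. The plan's own figure.** SE = 9 × √(2/35) = 2.15; 6/2.15 = 2.79; power 79.6%. The stated 80% reproduces, as a comparison of two means at one time with no baseline term.

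**2. Slope with a free arm term.** Mean time is 10.5 and the deviations are −10.5, −4.5, 1.5, 13.5, so Sxx = 315. For a 6-point step from week 6, slope = 6 × (−4.5 + 1.5 + 13.5)/315 = 63/315 = 0.20 points per week, or 24 × 0.20 = 4.8 points at week 24. That is 20% below 6. With √(1/70 + 1/35) = 0.207, the SE of the 24-week slope is 24 × 9 × √(1 − r)/√315 × 0.207 = 1.78 at r = 0.5.
- Step: 4.8/1.78 = 2.69, power 77%.
- Exactly linear rise to 6: 6/1.78 = 3.37, power 92%.

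**3. Baseline-adjusted week-24 contrast.** SE = 9 × √(1 − r²) × 0.207 = 1.61; 6/1.61 = 3.72; power 96% for either shape.

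**4. Dependence on r** (70 v 35, step effect):

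| r | Slope, free arm term | Week-24 adjusted |
|---|---|---|
| 0.5 | 77% | 96% |
| 0.6 | 85% | 98% |
| 0.7 | 94% | 99.5% |
| 0.8 | 99% | 100% |

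The 4.8 is the same in every row. The squared ratio of SEs, slope to adjusted, is (576/315)/(1 + r), which equals 1 at r = 0.83. Above that the slope is more precise: 0.80 v 0.81 at r = 0.9.

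**5. If SDMT is taken only at weeks 0, 12 and 24.** The protocol's schedules show no MACFIMS, the battery that contains the SDMT, at week 6. Aim 2 of the Analytic Plan and the SAP imply SDMT then. Without week 6, Sxx = 288 and an effect held from week 12 has slope 6 × 12/288 = 0.25, or 6.0 points, with no shrinkage. SE = 24 × 9 × √0.5/√288 × 0.207 = 1.86, and power is 90% against 96%.

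**6. Linear time with baseline means constrained equal.** The slope difference is then t′V⁻¹e/t′V⁻¹t, where e is the effect at each visit. At r = 0.5, V⁻¹ is proportional to I − 0.2J (J is the all-ones matrix). So t′V⁻¹t ∝ 756 − 0.2 × 42² = 403.2, and for the step t′V⁻¹e ∝ 6 × (42 − 0.2 × 42 × 3) = 100.8. The slope is 0.25, or 6.0 points. SE = 24 × 9 × √(0.5/403.2) × 0.207 = 1.57; power 97%. At r = 0.7 the multiplier 0.2 becomes 0.7/3.1 = 0.226, and the same step is estimated as 5.45 points with 98.8% power.

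Step 6 separates the two causes. At r = 0.5, constraining the baseline means recovers the whole power loss while time stays linear. The estimate still depends on the shape of the effect and on r.

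**The case against.** The strongest reply is that the SAP never says the arm term is free. With baseline means constrained equal, linear time costs no power at r = 0.5, so the 77% v 96% gap should not be laid at the door of linear time. That stands: much of the gap is baseline handling. But the free arm term is the conventional form of such a model, and the SAP does not state the constraint.

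Several stronger readings are tempting, and the documents do not support them:
- *The model ignores baseline.* It does not; week 0 is a response. What is missing is conditioning on it or constraining its mean.
- *The trial was sized on 6 SDMT points at r = 0.5.* The 29, the 35 and the 0.5 belong to the dementia-scale calculation. Six points is what that size can detect on SDMT.
- *The protocol predicts a plateau by week 6.* It mentions an acute effect and possible accumulation, and it places follow-up testing before the morning dose. The plateau is a scenario, not the stated expectation.
- *The test is biased or invalid.* Under the null it is valid. A slope is a different estimand, and it fits accumulating change.

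Plots of arm means, the visit-wise ANOVA and the spline analyses would also make a week-24 difference visible. That is true, but none of them changes which test is primary.

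**Conclusion.** The point holds as a mismatched and usually less efficient primary estimand. With a free arm term at r = 0.5 and 70 v 35, power is 77% v 96% for an early held effect and 92% v 96% for an exactly linear one, so the slope loses even when its own assumption is true. By r = 0.7 the slope exceeds 90% for the early held effect, and the power argument is weak from there up.

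The 20% understatement of a plateau does not depend on r, but it does depend on week-6 SDMT being collected, on a free arm term and on compound symmetry. If correlation instead decays with time to 0.5 at 24 weeks, the estimate is 5.93 points and power is 89% v 96%.

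No SDMT correlation is given, so the size of the loss is uncertain. The mismatch with the protocol's visit-level comparisons and 6-point difference does not depend on it. Because the trial's stated use is to inform phase III, it is worth correcting.

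**What to change.** In SAP VIII.g, treat visit as categorical with unstructured covariance. Constrain arm means equal at baseline, or adjust for baseline SDMT. Name the pooled-insulin v placebo difference at week 24 as the primary contrast, and keep the linear slope as supportive. State whether SDMT is collected at week 6, and restate power for 70 v 35 with an SDMT correlation and its range.

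This is a change of SAP wording only and uses data already planned. It should be dated before SDMT is compared by arm, since the protocol leaves the statistician unblinded. The statistical cost arises if the effect is truly linear: against the free-arm slope, the SE is about 2 to 3% larger at r = 0.9 to 0.95 (by the ratio in step 4 of the working, √(1.9/1.829) = 1.02 and √(1.95/1.829) = 1.03). If the sponsor prefers to keep linear time, stating the equal-baseline constraint alone would recover most of the power, but the estimate would still depend on the shape of the effect.

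### The primary test compares slopes, but random slopes enter only under an unspecified fit rule and the covariance is not pinned to one model; this can modestly understate the standard error

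*SAP*

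**What the plan says.** SAP section VIII.g analyses raw SDMT with a "linear mixed effects model with unstructured covariance structure, random intercepts" and linear time (VIII.f). It then states: "If model fit is improved with the addition of random slopes, they will be added". The tested quantity is the product of insulin and time. The same conditional rule is repeated in VIII.h for the other cognitive tests, the MSFC Z scores, the raw MSFC components, FAMS, sleep quality and depression, so it appears seven times.

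Section VIII does not give a fit criterion (AIC, BIC or a likelihood-ratio test), a threshold, a choice of ML or REML, or a degrees-of-freedom method. It also does not say whether *unstructured* describes the random effects or the residuals.

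The protocol's Analytic Plan fixes the random effects in advance for the Aim 1 safety comparisons, "using random subject-specific intercepts and slopes". For cognition (Aim 2) it names a longitudinal mixed model without specifying its random effects.

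**The concern.** A random-intercept model treats everyone in an arm as having the same true slope. If true slopes differ between people, that variation is part of the sampling error of the arm difference in slope, and the model leaves most of it out. The standard error is then too small and the test rejects too often. A fit rule removes the problem only in trials where it detects the variation. With about 105 participants and at most four visits, moderate variation is often missed.

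Pre-specification is also at stake. Two analysts could both follow this SAP, one using AIC and the other BIC, and report different primary p-values.

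**Working it through.** **1. The plan's own figure.** The protocol plans 35 per group ("a total of 35 subjects per group is planned") and states "With SDMT as the outcome, for a two-arm design, this sample size confers 80% power" "to detect a 6-point improvement in SDMT", "assuming SDMT standard deviation of 9 points and two-sided alpha of 0.05". Standard error: 9 × √(2/35) = 2.151. Then 6/2.151 = 2.789, and Φ(2.789 − 1.960) = 0.796. The stated 80% reproduces. It concerns a simple two-group comparison and does not involve slope variation.

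**2. Inputs for the slope test.** From the documents: SD 9, two-sided 0.05, pooled insulin against placebo at 70 v 35, weeks 0, 6, 12 and 24, linear time. Assumed, because the documents give no slope variance: an SD of true individual 24-week change of 0, 2, 4 or 6 points, and a between-visit correlation (before slope variation) of 0.5, 0.7 or 0.85. The protocol does use 0.5 ("assuming 3 follow-up cognitive tests and a correlation between baseline and follow-up results of 0.5, 29 subjects per group are required"), but for a dementia rating scale, not SDMT.

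**3. Error if slopes vary and are left out.** Let σ² = 81(1 − ρ), τ = (slope SD)/24, S = Σ(t − t̄)² = 315 and T = 4 visits. The ratio of the random-intercept standard error to the true one is

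√[(σ² + τ²S/(T − 1)) / (σ² + τ²S)],

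and the actual type I error is 2Φ(−1.96 × ratio). Example, ρ = 0.5 and slope SD 4: σ² = 40.5 and τ²S = 8.75, so the ratio is √(43.417/49.25) = 0.939 and the error is 6.6%.

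| Correlation | Slope SD 0 | 2 | 4 | 6 |
|---|---|---|---|---|
| 0.5 | 5.0% | 5.4% | 6.6% | 8.3% |
| 0.7 | 5.0% | 5.7% | 7.5% | 10.1% |
| 0.85 | 5.0% | 6.3% | 9.6% | 13.3% |

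These are for a random-intercept model that is never extended, which is not the SAP's rule.

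**4. Error under the SAP's rule.** Simulated null trials, complete data, REML, normal reference; 5,000 trials per row (Monte Carlo error about ±0.6 points):

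| Correlation, slope SD | AIC | LRT (2 df) | BIC | Slopes always | Slopes added (AIC/LRT/BIC) |
|---|---|---|---|---|---|
| 0.5, 4 | 6.1% | 6.3% | 6.9% | 5.3% | 43/26/4% |
| 0.7, 4 | 5.9% | 6.5% | 7.8% | 5.3% | 64/45/13% |
| 0.85, 2 | 5.7% | 5.9% | 6.2% | 5.1% | 27/14/1% |
| 0.85, 4 | 5.2% | 5.4% | 7.0% | 5.0% | 94/88/56% |

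A wider grid at 2,000 trials per cell (about ±1 point) peaked at 6.8% (AIC), 6.8% (LRT) and 8.3% (BIC). That was the last setting in the table, where always including slopes also read 6.6% by chance. With slope SD 0, the grid gave 4.8–5.7% under selection and 4.4–5.2% with slopes always included.

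A second parameterisation used intercept SD 8 and residual SD 4 (total SD √80 = 8.94, correlation 64/80 = 0.80). Repeated runs at slope SD 2–3 gave 5.1–6.1% with AIC and 5.6–7.1% with BIC.

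**5. What *unstructured* can mean.**
- Random-effects covariance: empty with an intercept alone, and an estimable 2×2 matrix once slopes are added.
- Residual covariance without random effects: estimable. Simulated error was 5.4–6.4% (3,000 trials per setting) with no trend in slope SD. The small excess comes from the normal reference in a small sample, not from omitted slopes.
- Random intercept plus an unstructured 4×4 residual matrix: 1 + 10 = 11 parameters for 10 distinct variances and covariances, so not identifiable.

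**The case against.** The strongest reply is that this is a matter of clarity with little effect on the result. Much of that stands.

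- *A reader might infer that the specified model cannot be estimated.* The documents do not support this. The natural reading is that *unstructured* refers to the random effects, and that model is estimable. Only the literal combination with an unstructured residual matrix fails. The fair statement is that the wording does not identify one model.
- *A reader might infer that the error rate can only rise.* It does not when slopes do not vary. In the second parameterisation, 15,000 trials with no slope variation gave 4.8–4.9% under selection and 4.1% with slopes always included, so selection was the closer to nominal.
- *A reader might take the 10–13% figures as the risk.* They belong to a model that never gains slopes. At correlation 0.85 and slope SD 6, every criterion added slopes in essentially all trials, and the error was 5.4%. Likewise, the random-intercept figures for the secondary week-48 analysis (7.6–29.8% when slopes vary) were not computed under selection.
- *A reader might see a contradiction with the protocol.* There is none. The fixed random slopes are for Aim 1 safety, and Aim 2 leaves the choice open.
- The larger assumed slope SDs are demanding. Values of 4–6 points equal or exceed the 3.5–4 points that the protocol's Cognitive Assessments section calls clinically meaningful.
- Week 6 SDMT data are uncertain. The visit schedules omit the MACFIMS battery at week 6, while the Aim 2 analysis and the SAP use SDMT there. With visits at 0, 12 and 24 only, error under AIC was 4.8–5.6%.
- The protocol itself does not expect conclusive efficacy evidence.

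What survives is that no criterion is stated, the choice is made on the trial data, and when slopes vary moderately the rule often keeps the smaller standard error.

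**Conclusion.** The concern holds as a modest, conditional one. The standard error of the primary term depends on an unspecified, data-driven choice. When true slopes vary and the rule misses it, that standard error is too small. Under assumed slope SDs of 2–6 points per 24 weeks, week-24 type I error is about 5–7% with AIC or a likelihood-ratio test and up to about 8% with BIC, against about 5% with slopes always included. These figures rest on complete, balanced data and on slope variances that the documents do not supply. If slopes do not vary, or if an unstructured residual matrix without random effects is intended, this mechanism adds nothing. It is a cheap improvement and does not undermine the trial.

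**What to change.** Delete the fit condition in all seven places and state one model in SAP section VIII for every slope analysis. Suggested text:

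> Random intercept and random slope for time, with an unstructured 2×2 random-effects covariance and independent residuals, fitted by REML with Kenward-Roger degrees of freedom. If the fit does not converge, the intercept-slope covariance is set to zero; if that also fails, a random-intercept model with a robust standard error is used. A singular (boundary) fit is retained and does not trigger the fallback.

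The last sentence is needed. In the second parameterisation the random-slope fit was singular in 54% of trials at slope SD 0 and 26% at slope SD 2, so a fallback that included singular fits would bring back a data-driven choice. Naming a criterion instead would remove the ambiguity but leave the selection effect.

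The cost is a short SAP edit and no new data. If slopes vary little or not at all, type I error is about 4–5%. Power falls by about 1–2 points: for an illustrative effect of 2.5 points over 24 weeks, 58.8% against 60.2% with AIC at slope SD 0, and 54.9% against 57.0% at slope SD 2.
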